#### 8.1.5 Analysis Data for Regulatory Submission

Data collected during this study as well as the derived data will be formatted to meet the SDTM (Study Data Tabulation Model) and the Analysis Data Model (ADaM) standards of Clinical Data Interchange Standards Consortium (CDISC). A standard Define.doc file that describes the data attributes will be provided,

## 9 STATISTICAL METHODS

### 9.1 GENERAL STATISTICAL CONSIDERATIONS

All statistical summaries and analyses will be performed using SAS® for Windows, version 9.4 or later.

Collected study data will be presented in subject data listings.

For continuous variables descriptive statistics (n, mean, standard deviation, median, minimum and maximum) will be presented by treatment group.

For categorical variables data summaries by treatment group will include frequency counts and percentages.

Formal treatment group comparisons will be made at the nominal two-sided 0.05 level of significance using the FAS and PP analysis sets. The 95% confidence intervals and p-values for comparing treatment groups will be computed.

#### 9.1.1 Mock Table Shells

A separate document will be created that describes the format of the statistical Listings and Tables (i.e. mock table shells)

#### 9.1.2 Covariates

For efficacy analyses the baseline values will be used as a covariate.

#### 9.1.3 Protocol Deviations

Subject listing of major protocol deviations by treatment group will be provided.

#### 9.1.4 Analysis sets

The number of subjects in each analysis set will be computed for each part of the study and treatment group and overall.

#### Number of Subjects in Analysis Set

## STATISTICAL ANALYSIS PLAN (SAP) CD1-NASH-01

Protocol No. CD1-NASH-01      Revision No. Rev. 00      Effective Date: 17-Dec-2021

	PART 1			PART 2
	PLACEBO	LERONLIMAB 700 MG	OVERALL	LERONLIMAB 350 MG
Full Analysis set (FAS)	n	n	n	n
Per protocol set (PP)	n	n	n	n
Safety analysis set	n	n	n	n

### 9.1.5 Subject Disposition and Withdrawals

The disposition of all subjects who sign an ICF will be provided. The numbers of subjects screened, randomized, received treatment, completed study, terminated early, and reasons for termination will be listed and/or summarized by treatment group.

#### Summary of Subject Disposition

	PLACEBO N (%)	PART 1	PART 2
		LERONLIMAB 700 MG N (%)	LERONLIMAB 350 MG N (%)
Assessed for screening	n (xx)	n (xx)	n (xx)
Eligible at screening	n (xx)	n (xx)	n (xx)
Ineligible at screening	n (xx)	n (xx)	n (xx)
Eligible and randomised	n (xx)	n (xx)	n (xx)
Received randomized therapy	n (xx)	n (xx)	n (xx)
Not received randomized therapy	n (xx)	n (xx)	n (xx)
End of Treatment	n (xx)	n (xx)	n (xx)
Early Termination	n (xx)	n (xx)	n (xx)
ET – LTFU	n (xx)	n (xx)	n (xx)
ET- PATIENT WISH	n (xx)	n (xx)	n (xx)
ET – AE	n (xx)	n (xx)	n (xx)
ET - Other	n (xx)	n (xx)	n (xx)

### 9.1.6 Demographic and Baseline Disease Characteristics

Demographics and baseline disease characteristics medical history, prior and concomitant medications/therapies will be summarized by treatment group

The following variables will be summarized descriptively using frequency counts and/or summary statistics n, mean, sd, median, min and max, as appropriate:

VARIABLE	TYPE	PRESENTATION
Age	CONT	In years
Gender	CAT	Male vs Female
Racial categories	CAT	Non-Hispanic Caucasian Hispanic Black/African American Asian Natives Other

## STATISTICAL ANALYSIS PLAN (SAP) CD1-NASH-01

Protocol No. CD1-NASH-01      Revision No. Rev. 00      Effective Date: 17-Dec-2021

BMI	CONT	Continuous
BMI category	CAT	Underweight : <18.5 Healthy weight : 18.5 – 24.9 Overweight : 25.0 – 29.9 Low risk obesity : 30.0 – 34.9 Moderate risk obesity : 35.0 – 39.9 High risk obesity : >=40.0
Blood pressure	CAT	Hypertension: Systolic>=140 and Diastolic>=90 No hypertension : All other combinations
Heart rate	CAT	Slow : <60 beats per minute Normal : 60-100 beats per minute Fast :>100 beats per minute
Alcohol consumption	CAT	Never/Current/Former
Duration NASH diagnosis	CONT	Duration in years
Nash medication	CAT	None/unknown/yes
Stage Liver Fibrosis histology	CAT	F0/F1/F2/F3/F4/Unknown
Stage Steatosis histology	CAT	S0/S1/S2/S3
Stage Steatosis CAP US	CAT	S1 238-260 S2 260-290 S3 >290
Stage Fibrosis US	CAT	F0-F1 2-7 F2 7.5 -10 F3 10 – 14 F4 >14
cT1	CONT	
PDFF	CONT	
Co-morbidities	CAT	Yes/No
Number of co-morbidities	CAT	0-5 5-10 10-15 15-20 20-25 >25
Concomitant medication	CAT	Yes/No
Number of concomitant medications	CAT	0-5 5-10 >10

### 9.1.7 Alcohol Consumption and Related Variables

For the patient population entering the study alcohol consumption variables will be summarized as follows:

#### Summary of Alcohol Consumption and Related Variables

PART 1

PART 2

## STATISTICAL ANALYSIS PLAN (SAP) CD1-NASH-01

Protocol No. CD1-NASH-01	Revision No. Rev. 00	Effective Date: 17-Dec-2021
-----------------------------	-------------------------	--------------------------------

ALCOHOL CONSUMPTION	PLACEBO (N=NN)	LERONLIMAB 700 MG (N=NN)	LERONLIMAB 350 MG (N=NN)
Never	n (xx%)	n (xx%)	n (xx%)
Current	n (xx%)	n (xx%)	n (xx%)
Former	n (xx%)	n (xx%)	n (xx%)

### 9.1.8 Medical History

Medical history of the subjects will be listed and summarized by treatment group.

#### Summary of Medical History N (%)

PLACEBO (N=NN)	PART 1	PART 2
	LERONLIMAB 700 MG (N=NN)	LERONLIMAB 350 MG (N=NN)
n (xx%)	n (xx%)	n (xx%)
n (xx%)	n (xx%)	n (xx%)
n (xx%)	n (xx%)	n (xx%)

### 9.1.9 Concomitant Medications

Concomitant medications will be coded using WHO dictionary. Concomitant medications will be listed and summarized by treatment group and ATC levels 1 and 2:

#### Concomitant Medications N (%)

PLACEBO (N=NN)	PART 1	PART 2
	LERONLIMAB 700 MG (N=NN)	LERONLIMAB 350 MG (N=NN)

#### Anatomic Group

#### Therapeutic subgroup

#### Preferred Drug Name

#### Alimentary Tract and

#### Metabolism

#### Drugs For Acid Related

#### Disorders

OMEPRAZOLE

RANITIDINE

n (xx)

n (xx)

n (xx)

n (xx)

n (xx)

n (xx)

## STATISTICAL ANALYSIS PLAN (SAP) CD1-NASH-01

Protocol No. CD1-NASH-01	Revision No. Rev. 00	Effective Date: 17-Dec-2021
-----------------------------	-------------------------	--------------------------------

## 9.2 Analysis of efficacy data

Data for each part of the study will be analysed separately. For Part 1 of the study leronlimab 700mg group will be compared to placebo. For Part 2 of the study leronlimab 350mg group will be compared to placebo from Part 1.

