3 STUDY DESIGN

This is a phase II, multi-center, two-part study (Part 1: randomized, double-blind, placebo-controlled, two-arm with 60 patients; Part 2: non-randomized, single-arm, open-label with 30 patients) designed to evaluate the safety and efficacy of leronlimab (PRO 140) SC in patients with NASH for 13 weeks. In Part 1 of the study, leronlimab (PRO 140 at 700 mg dose) or placebo will be weekly administered subcutaneously by a licensed healthcare professional at the clinic sites.

A single arm, non-randomized, open-label phase (Part 2) is added to the protocol after completion of enrollment in the Randomized Phase (Part 1) of the study. In Part 2 of the study, leronlimab (PRO 140 350 mg dose) will be weekly administered subcutaneously (SC) by a licensed healthcare professional at the clinic sites.

- **Part 1:** randomized, double-blind, placebo-controlled, two-arm (up to 60 subjects)
 - Leronlimab (PRO 140 700 mg) or Placebo SC weekly injection for 13 weeks
- **Part 2:** non-randomized, open-label, single-arm (up to 30 subjects)
 - Leronlimab (PRO 140 350 mg) SC weekly injection for 13 weeks

This study consists of screening, treatment, and follow-up periods.

The study flow diagram is presented in [Figure 3-1](#).

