8.7 GENERAL STATISTICAL CONSIDERATIONS

All collected study data will be presented in subject data listings. Statistical analyses will be performed using SAS® for Windows, version 9.4 or later. Descriptive statistics (n, mean, standard deviation, median, minimum and maximum) will be presented by treatment group for continuous variables. Frequencies and percentages will be presented by treatment group for categorical variables.

Analysis Populations

Intent-to-Treat Population

The **Intent-to-Treat (ITT) population** is defined as the set of subjects who have received at least one dose of study treatment (Leronlimab (PRO 140) or placebo) and have at least one post-baseline efficacy assessment. The ITT population will be used as the primary analysis population.

Per Protocol Population

The **Per Protocol (PP) population** is defined as the set of subjects who meet the ITT population requirements, were not associated with any major protocol violations and have at least 80% of compliance with study treatment. This population will be identified before the database lock.

The PP analysis of primary and secondary endpoints will be considered supportive.

Safety Population

The **Safety Population** will include all subjects who have received one dose of study treatment (Leronlimab (PRO 140) or placebo). This population will be used for the analysis of safety parameters.

Covariates

For efficacy analyses, the baseline values will be used as covariates in the analysis models. Other important prognostic factors will be specified in the SAP for the study.

Missing Data

All data will be used as observed, and no imputations will be made for any missing data point for early phase study.

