## 2.7 Randomization

Part 1:

Subjects who are eligible to participate in the trial will be randomized 1:1 to one of the treatment groups via IWRS (Interactive Web Based Randomization System) at the Visit prior to IP administration. The randomization will be central and will use 1:1 ratio of Treatment groups

- Leronlimab 700mg SC weekly injection
- Placebo 0mg SC weekly injection

Part 2:

Randomization is not applicable for the open-label, single-arm portion (Part 2) of the study.

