### 3.2 Secondary Endpoints

The secondary endpoints for Part 1 of the study are

- Change from baseline in fibro-inflammatory activity as assessed by cT1 (corrected T1) assessed by multiparametric magnetic resonance imaging (MRI) of liver at week 14 (Note: cT1 measured in milliseconds is a quantitative metric for assessing a composite of liver inflammation and fibrosis) fibrosis).
- Change from baseline in liver fibrosis using FibroTest at week 14
- Change from baseline in hepatic inflammatory activity using FibroTest at week 14
- Change from baseline in serum pro-inflammatory biomarkers assessments
- Change from baseline in Gamma-glutamyltransferase (GGT) at week 14
- Change from baseline in Cytokeratin 18 (CK-18) level at week 14
- Change from baseline in Leronlimab (PRO 140) PK assessments

	STATISTICAL ANALYSIS PLAN (SAP) CD1-NASH-01		
	Protocol No. CD1-NASH-01	Revision No. Rev. 00	Effective Date: 17-Dec-2021

The secondary endpoints for Part 2 of the study are:

- Change from baseline in fibro-inflammatory activity as assessed by cT1 (corrected T1) assessed by multiparametric magnetic resonance imaging (MRI) of liver at week 14 (Note: cT1 measured in milliseconds is a quantitative metric for assessing a composite of liver inflammation and fibrosis) compared to part 1 placebo
- Change from baseline in liver fibrosis using FibroTest at week 14 compared to Part 1 placebo
- Change from baseline in hepatic inflammatory activity using FibroTest at week 14 compared to Part 1 placebo
- Change from baseline in serum pro-inflammatory biomarkers assessments compared to Part 1 placebo
- Change from baseline in Gamma-glutamyltransferase (GGT) at week 14 compared to Part 1 placebo
- Change from baseline in Cytokeratin 18 (CK-18) level at week 14 compared to Part 1 placebo
- Change from baseline in Leronlimab (PRO 140) PK assessments compared to Part 1 placebo

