### 9.2.1 Analysis of Primary Efficacy Endpoint

The null hypothesis of no between treatment group difference in mean change from baseline in hepatic fat fraction assessed by magnetic resonance imaging-derived proton density fat fraction (MRI-PDFF) at week 14 against alternate hypothesis of a non-zero treatment-difference will be tested at 0.05 level of significance.

A preliminary assessment of normality will be performed using Shapiro-Wilks test at the 5% significance level.

If departure from normality is not concluded a normality-based parametric test of the null hypothesis will be performed using ANCOVA with baseline as a continuous covariate and treatment group as a categorical covariate. The point estimate of the mean (SD) along with corresponding 95% confidence interval will be presented. The baseline adjusted estimates of the treatment means and treatment difference along with 95% confidence interval and the two-sided p-values will be presented.

Otherwise, the null hypothesis will be tested using the two-sample Wilcoxon Rank Sum test and the Hodges-Lehmann estimate of location shift along with the corresponding 95% confidence intervals will be reported.

Even if the parametric analysis is deemed appropriate, the non-parametric analyses will be performed to assess the robustness of the conclusions based on ANCOVA.

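### The open-label, non-randomised 350 mg arm is formally tested against the Part 1 placebo arm at two-sided 0.05, a level that nothing in the design secures for that comparison

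*SAP*

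**What the plan says.** SAP 2.2 and 9.2 set the comparator for Part 2: "For Part 2 of the study leronlimab 350mg group will be compared to placebo from Part 1". SAP 3.2 builds that comparator into every Part 2 secondary endpoint, for example "Change from baseline in liver fibrosis using FibroTest at week 14 compared to Part 1 placebo".

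On how Part 2 came about, Protocol section 3 says that the single-arm phase "is added to the protocol after completion of enrollment in the Randomized Phase (Part 1) of the study". SAP 2.7 notes that "Randomization is not applicable for the open-label, single-arm portion (Part 2) of the study", and SAP 2.8 says the same of blinding.

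On inference, SAP 9.1 states: "Formal treatment group comparisons will be made at the nominal two-sided 0.05 level of significance using the FAS and PP analysis sets". It asks for confidence intervals and p-values and makes no exception for Part 2. Programming notes repeat three sets of p-value tables for 350 mg against Part 1 placebo:
- the MRI-PDFF tables, ANCOVA and non-parametric (9.2.1);
- the cT1 category table with its CMH test (9.2.2);
- the biomarker interaction table (9.2.4).

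On adjustment, Protocol 8.7 promised that "Other important prognostic factors will be specified in the SAP for the study". SAP 9.1.2 gives only this: "For efficacy analyses the baseline values will be used as a covariate". If normality is rejected, "the null hypothesis will be tested using the two-sample Wilcoxon Rank Sum test", which takes no covariate.

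**The concern.** In Part 1, randomisation is what makes a 0.05 test reject a true null 5% of the time. The 350 mg comparison has no such support. The two cohorts were enrolled at different times, and one of them knew it was on active drug. Placebo subjects were blinded and had two injections a week; 350 mg subjects have one.

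MRI-PDFF is an objective reading, but liver fat itself responds to behaviour. Protocol 1.2 says that lifestyle change helps steatosis, and the stable-diet requirement sits only under the inclusion criterion for pre-diabetes and type 2 diabetes.

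The per-protocol analyses add a further weakness. Several exclusions in SAP 2.9.1 rest on investigator judgement. The safeguard of classifying deviations before unblinding has no force in an open-label arm.

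At stake is how the 350 mg results are read. They would appear with p-values in the same format as the randomised 700 mg results, and nothing would mark them as weaker evidence. A cohort difference could give false support to 350 mg, or mask a real effect.

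**Working it through.** **Inputs from the documents.** Two-sided level 0.05 (SAP 9.1). Group sizes of 30 placebo and up to 30 on 350 mg (SAP 4). Neither document gives an SD, an effect size or a dropout rate, and Protocol 8.3 says the sample size has no power basis.

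**Assumptions.** A cohort shift *d* is the difference between the Part 2 and Part 1 cohorts that is not due to drug, in SD units of the analysed change. It is varied from 0 to 0.5. A size of 25 per group is also shown, to allow for losses.

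**Formula.** For a two-sample t test with no drug effect, the noncentrality is *d* / √(1/n₁ + 1/n₂). The rejection rate is the probability that a noncentral t with n₁ + n₂ − 2 degrees of freedom falls outside the two-sided 5% critical values. With 30 per group, √(2/30) = 0.258.

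**Reproducing the plan's figure.** At *d* = 0 the rejection rate is 0.050, so the stated level holds if the cohorts do not differ.

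**Results with an inactive drug.**

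| Shift *d* (SD) | Noncentrality, 30/30 | Rejection rate, 30/30 | Rejection rate, 25/25 | 95% CI coverage, 30/30 |
|---|---|---|---|---|
| 0 | 0 | 0.050 | 0.050 | 0.95 |
| 0.1 | 0.387 | 0.067 | 0.064 | 0.93 |
| 0.2 | 0.775 | 0.119 | 0.107 | 0.88 |
| 0.25 | 0.968 | 0.159 | 0.139 | 0.84 |
| 0.4 | 1.549 | 0.331 | 0.283 | 0.67 |
| 0.5 | 1.936 | 0.478 | 0.410 | 0.52 |

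Coverage of the true drug difference is one minus the rejection rate.

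**Hand check at 0.25 SD**, normal approximation: Φ(−1.96 + 0.968) + Φ(−1.96 − 0.968) = 0.162, against 0.159 from the noncentral t.

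**Check with the planned methods.** In 20,000 simulated trials (30/30, normal residuals), baseline-adjusted ANCOVA rejected in 0.161 at 0.25 SD and 0.470 at 0.5 SD. The Wilcoxon test rejected in 0.154 and 0.449.

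**Shift in the opposing direction.** For an assumed true effect of 0.75 SD (30/30), power is 0.815 with no shift. It falls to 0.697 with an opposing 0.1 SD, which leaves 0.65 SD. It falls to 0.478 with an opposing 0.25 SD, which leaves 0.50 SD.

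**The case against.** The case for leaving the plan alone has real content.

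- **The level is called nominal, and the sample size is justified for descriptive results.** Both are true. But the same sentence of SAP 9.1 calls the comparisons formal and asks for p-values, and nothing labels the Part 2 p-values as descriptive. The sample-size wording supports the change rather than the test.
- **Little turns on it.** SAP 3.1 names a primary endpoint for Part 1 only, and neither document ties a decision rule to a 350 mg p-value. This stands, and it limits how serious the point is.
- **The design is disclosed, and the Part 2 efficacy tables are separate.** True, but disclosing the design elsewhere does not settle the status of a p-value produced under a rule for formal tests.
- **The sizes are generic.** This stands. The curve would fit any external control of this size, and nothing in the documents supports 0.4 or 0.5 SD in particular. Shared eligibility, the shared visit schedule, an MRI endpoint and baseline adjustment in the ANCOVA all reduce the likely shift. They do not make it zero.
- **The comparison was implied.** The protocol title speaks of three arms and dose-ranging, its objectives refer to placebo, and the only placebo arm is in Part 1. Whether SAP section 10 had to list the comparison is therefore debatable, though listing it costs nothing.
- **Missing baseline adjustment in the Wilcoxon, CMH and biomarker analyses also affects Part 1.** True, but in Part 1 randomisation protects the error rate without it.
- **A CI that excludes zero reads like a test.** Also true, which is why the fix needs explicit wording as well as the removal of p-values.

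**Conclusion.** The concern holds. As written, the SAP produces 350 mg p-values and confidence intervals whose error rates have no basis in the design. The claim is that 5% is not assured, not that it is wrong by a known amount. Under assumed shifts of 0.1 to 0.5 SD with 30 per group, the false-positive rate runs from 6.7% to 48%. An opposing shift of 0.25 SD cuts power for an assumed 0.75 SD effect from 82% to 48%. These figures rest entirely on the assumed shift, because the documents give nothing from which to estimate it. The randomised 700 mg comparison is not touched. The plan should be corrected, but the defect does not undermine the trial's primary result.

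**What to change.** 1. **SAP 9.1:** state that the two-sided 0.05 test applies only to 700 mg versus placebo in Part 1.
2. **SAP 2.2, 3.2 and 9.2, for Part 2:** report the within-arm change on 350 mg with a 95% CI, and the difference from Part 1 placebo with a 95% CI. Take the difference from a model with baseline outcome, age, sex, BMI and diabetes status. State a rule for deriving diabetes status from the medical history, medication or HbA1c data already collected. Label the result exploratory, non-randomised and non-concurrently enrolled. Say that the interval does not reflect cohort bias and is not to be read as a test.
3. **Repeated Part 2 tables:** drop the p-values. In 9.2.1 show the adjusted difference and the Hodges-Lehmann shift, each with a CI, and mark the latter as unadjusted. In 9.2.2 show cT1 category frequencies. In 9.2.4 show interaction coefficients with CIs.
4. **SAP section 10:** list the cross-part comparison.

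The cost is SAP wording, three programming notes and four extra covariates in the Part 2 model. The covariates are a proposal; the documents do not name them as prognostic. The sponsor gives up nominal p-values for 350 mg. Adjustment cannot remove effects of calendar time or open-label behaviour, so the label is needed as well as the model.

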### 9.2.1 Analysis of Primary Efficacy Endpoint

The null hypothesis of no between treatment group difference in mean change from baseline in hepatic fat fraction assessed by magnetic resonance imaging-derived proton density fat fraction (MRI-PDFF) at week 14 against alternate hypothesis of a non-zero treatment-difference will be tested at 0.05 level of significance.

A preliminary assessment of normality will be performed using Shapiro-Wilks test at the 5% significance level.

If departure from normality is not concluded a normality-based parametric test of the null hypothesis will be performed using ANCOVA with baseline as a continuous covariate and treatment group as a categorical covariate. The point estimate of the mean (SD) along with corresponding 95% confidence interval will be presented. The baseline adjusted estimates of the treatment means and treatment difference along with 95% confidence interval and the two-sided p-values will be presented.

Otherwise, the null hypothesis will be tested using the two-sample Wilcoxon Rank Sum test and the Hodges-Lehmann estimate of location shift along with the corresponding 95% confidence intervals will be reported.

Even if the parametric analysis is deemed appropriate, the non-parametric analyses will be performed to assess the robustness of the conclusions based on ANCOVA.

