8.8 ANALYSIS METHODS

A SAP will be developed and approved before the database is locked. The SAP will present the detailed statistical methodology to be used in analyzing the data from this trial. All inferential statistical analysis will be based on a two-sided test with a Type I error rate of 0.05.

All the efficacy analyses presented here will be conducted using both the ITT and PP populations. All safety analyses will be conducted using the Safety population. Continuous data summaries will

include number of observations, mean, standard deviation, median, and minimum and maximum values. Categorical data summaries will include frequency counts and percentages.

Subject Disposition

The disposition of all subjects who sign an ICF will be provided. The numbers of subjects screened, randomized, received treatment, completed, and discontinued during the study, as well as the reasons for all post-enrollment discontinuations will be listed and/or summarized by treatment group.

Demographic and Baseline Disease Characteristics

Demographics and baseline disease characteristics including medical history, prior and concomitant medications/therapies will be listed and/or summarized by treatment group using appropriate descriptive statistics.

Study Analyses

Efficacy Analysis

Analysis of the efficacy endpoints will be conducted according to below methods:

- If the Normality assumption is met, Analysis of Covariance (ANCOVA) or Mixed Model using the covariates in the model.
- If the Normality assumption is not met, a non-parametric method or a rank – ANCOVA analysis will be used.

Safety Analyses

Safety will be assessed by close monitoring and timely assessment of adverse events (AEs), laboratory parameters (blood tests, urinalysis), vital signs (blood pressure, heart rate), subject's medical condition (physical examination including weight). Tolerability of repeated subcutaneous administration of Leronlimab (PRO 140) as assessed by study participants (using 11-point Numeric Pain Rating Scale) and by investigator-evaluation of injection site reactions.

Adverse Events

Adverse events will be coded using the most recent version of Medical Dictionary for Regulatory Activities (MedDRA). Treatment Emergent AE's (TEAE) are defined as events with an onset on or after the first treatment. TEAEs will be summarized by treatment group, System Organ Class, and preferred term. The following TEAE summaries will be provided:

- by PT in descending order of frequency

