#### Summary of MRI-PDFF Method: ANCOVA

	PART 1			
	PLACEBO (N=NN)	LERONLIMAB 700MG (N=NN)	DIFFERENCE 95%CI (Lower-Upper)	P-VALUE [1]
Number. of Subjects	nn	nn		
Baseline	xx.x (xx.x)	xx.x (xx.x)		
Week 14	xx.x (xx.x)	xx.x (xx.x)		
Change at WK14	xx.x (xx.x)	xx.x (xx.x)		
Baseline Adjusted Change at WK14	xx.x (xx.x)	xx.x (xx.x)	xx.xxx (xx.x) (xx.xxx-xx.xxx)	0.xxx

[1] p-value computed using ANCOVA accounting for treatment and baseline as covariates.

\*Programming note 1: Create similar tables for Method=Non-parametric, change headers and footers accordingly.

\*Programming note 2: Repeat these tables for Part 2.

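### The Wilcoxon fallback and robustness test in SAP 9.2.1 drop the baseline covariate: this costs some Part 1 power if errors are non-normal, and in Part 2 adjusted and unadjusted results should stand side by side

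*SAP*

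**What the plan says.** SAP 9.2.1 opens the primary analysis with a normality test: "A preliminary assessment of normality will be performed using Shapiro-Wilks test at the 5% significance level". It does not say whether the test is applied to raw change, to each arm, or to model residuals. If normality is not rejected, the test is ANCOVA with baseline and treatment. If it is rejected: "Otherwise, the null hypothesis will be tested using the two-sample Wilcoxon Rank Sum test and the Hodges-Lehmann estimate of location shift". Neither the Wilcoxon test nor the Hodges-Lehmann estimate carries a covariate. The same analysis also serves as a check on ANCOVA: "Even if the parametric analysis is deemed appropriate, the non-parametric analyses will be performed to assess the robustness of the conclusions based on ANCOVA".

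The general rule in SAP 9.1.2 has no exception: "For efficacy analyses the baseline values will be used as a covariate". Protocol 8.7 is close to it: "For efficacy analyses, the baseline values will be used as covariates in the analysis models". Protocol 8.8 leaves the fallback open: "If the Normality assumption is not met, a non-parametric method or a rank"-ANCOVA analysis.

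The rule reaches further than Part 1 MRI-PDFF. SAP 9.2.2 and 9.2.3 apply like methods to cT1 and to the other continuous secondary and exploratory endpoints. On Part 2, SAP 9.2 states: "For Part 2 of the study leronlimab 350mg group will be compared to placebo from Part 1". A note under the MRI-PDFF table shell adds: "Programming note 2: Repeat these tables for Part 2". That is how a Part 2 PDFF comparison enters: SAP 3.1 makes PDFF primary for Part 1 only, and SAP 3.2 lists no PDFF endpoint for Part 2.

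**The concern.** Whether baseline is adjusted for depends on the outcome of a normality test. There are three consequences.

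- **Part 1 power.** Leaving out a prognostic covariate wastes information that has already been collected.
- **Part 1 robustness check.** It changes the covariate and the distributional assumption together. A disagreement with ANCOVA cannot be traced to either.
- **Part 2.** The 350 mg group was added after Part 1 enrolment was complete and is not randomised against Part 1 placebo. Baseline may differ between the two, so the choice between adjusting and not adjusting can decide the result.

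**Working it through.** **Inputs from the documents.** 30 per arm in Part 1 and up to 30 in Part 2 (protocol 8.3, SAP 4); two-sided 0.05 (protocol 8.8); Shapiro-Wilk at 5% (SAP 9.2.1). No power, SD, correlation or error shape is given, so there is no plan figure to reproduce and every size below is conditional.

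**Assumptions.** Equal SDs at baseline and week 14; correlation ρ between them of 0.3 to 0.9; errors normal, Student t with 5 or 3 degrees of freedom (t5, t3), or skewed (gamma, shape 2); Shapiro-Wilk on ANCOVA residuals. For power, the effect is set so that ANCOVA has 79 to 81%.

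**Step 1: what dropping baseline costs.** With common SD σ, the variance of change is 2(1−ρ)σ² and the ANCOVA residual variance is (1−ρ²)σ². Their ratio is (1−ρ²)/[2(1−ρ)] = (1+ρ)/2. This is the relative efficiency of unadjusted change: 0.65, 0.75, 0.85, 0.90 and 0.95 at ρ = 0.3, 0.5, 0.7, 0.8 and 0.9. The loss is large at low ρ and small at 0.9.

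**Step 2: Part 1 by simulation** (6,000 trials per cell; Monte Carlo SE about 0.5 points for power and 0.3 for type I error). Null rejection over all procedures was 4.2 to 6.0%. Shapiro-Wilk rejected in about 5% of trials with normal errors, 37–39% with t5, 66–69% with t3 and 94–96% with skewed errors.

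| ρ | Power gain of rank-ANCOVA fallback over the written procedure, non-normal errors (points) | Wilcoxon check contradicts ANCOVA, normal errors, ANCOVA kept |
|---|---|---|
| 0.3 | 6–17 | 23–25% |
| 0.5 | 4–12 | 17–19% |
| 0.7 | 2–6 | 13–14% |
| 0.8 | 1–4 | 11% |
| 0.9 | 1–2 | 8–9% |

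Rank-ANCOVA contradicts ANCOVA in about 6 to 8% of trials (5 to 8% in one run). With normal errors its power gain as fallback is 0 to 1 point. A repeat simulation gave gains of 2 to 17 points with skewed errors and 1 to 13 with t3.

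A separate check used exponential errors, a 0.5 SD effect and the baseline-to-change correlation r. Under equal SDs, r = −√[(1−ρ)/2], so ρ = 1 − 2r². At r = −0.5, ρ = 1 − 2(0.25) = 0.5: power was 57% as written and 74% with rank-ANCOVA, a gain of 17 points. At r = −0.3, ρ = 1 − 2(0.09) = 0.82: 67% against 73%, a gain of 6 points. Its third setting, r = −0.7, implies ρ = 1 − 2(0.49) = 0.02 and is set aside as implausible.

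**Step 3: Part 2, no drug effect, baseline gap d.**

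- If both groups regress to a common mean, the expected difference in change is −(1−ρ)d and the adjusted difference is 0.
- If the gap is a stable cohort difference, the expected difference in change is 0 and the adjusted difference is +(1−ρ)d.

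The two biases are mirror images. With an assumed d of 0.5 SD, each is 0.35, 0.25, 0.15, 0.10 and 0.05 SD across the same ρ values. Rejection rates (%) at that gap:

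| Reason for the gap | Procedure | ρ 0.3 | 0.5 | 0.7 | 0.8 | 0.9 |
|---|---|---|---|---|---|---|
| Regresses to common mean | Written, t3 or skewed | 18–22 | 15–18 | 11–12 | 9–10 | 7–8 |
| Regresses to common mean | Rank-ANCOVA fallback | 5–6 | 5–6 | 5–6 | 5–6 | 5–6 |
| Stable cohort gap | Written, skewed | 6.8 | 5.7 | 5.7 | 5.8 | 4.9 |
| Stable cohort gap | Written, t3 | 16.7 | 12.5 | 9.6 | 7.3 | 6.2 |
| Stable cohort gap | Rank-ANCOVA fallback, skewed | 30.0 | 20.5 | 13.0 | 10.2 | 7.2 |
| Stable cohort gap | Rank-ANCOVA fallback, t3 | 38.1 | 26.2 | 16.4 | 12.5 | 8.1 |

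The repeat simulation gave 7–21% for the written procedure under regression to a common mean. Under a stable gap it gave 5–17% as written and 7–37% with rank-ANCOVA. The written procedure is not clean in the stable case either: with t3 errors Shapiro-Wilk misses about a third of trials, and those keep the biased ANCOVA.

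**The case against.** The strongest reply is that protocol 8.8 allows any non-parametric method, SAP 9.2.1 is the specific rule and 9.1.2 the general one, and a two-sample Wilcoxon test has no model in which to place a covariate. The tested variable is change, so baseline is at least subtracted. Wilcoxon with Hodges-Lehmann is a matched test and interval. With non-normal errors and ρ of 0.7 to 0.9, the written procedure gains 1 to 11 points over ANCOVA. The study was sized by clinical judgment for descriptive results.

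Much of this stands. A reader might infer a breach of the protocol; protocol 8.8 rules that out. What remains is an inconsistency with SAP 9.1.2 when a named option would have met both. The gain over ANCOVA at high ρ is real, but rank-ANCOVA adds 1 to 6 points more there, and more still at low ρ.

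A reader might also infer that Part 2 is where the harm lies and that rank-ANCOVA should replace Wilcoxon there. The false-positive rates of up to about 20% behind that reading assume regression to a common mean. The documents do not say why a non-randomised cohort's baseline would differ. If the gap is stable, the replacement makes matters worse. In that setting an unadjusted result beside ANCOVA is informative, because disagreement shows that the conclusion depends on adjustment.

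**Conclusion.** The point holds in limited form. SAP 9.2.1 drops baseline in the fallback and in the robustness test, against SAP 9.1.2, and leaves the variable for Shapiro-Wilk unstated.

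Part 1 is not invalid. Its cost is power, and only under non-normal errors: about 1 to 17 points under the assumptions above, smallest at high correlation. With normal errors the effect is on the robustness check, which contradicts ANCOVA in about 9 to 25% of trials instead of 6 to 8%.

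For Part 2 the documents support neither analysis alone. Neither adjusts for unmeasured cohort differences.

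Because the choice is permitted, Part 1 keeps its error rate and every size rests on inputs outside the documents, this is a change to consider.

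**What to change.** Amend SAP 9.2.1 before database lock and unblinding.

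1. For Part 1, and the Part 1 endpoints that inherit the rule through 9.2.2 and 9.2.3, use rank-ANCOVA (ranks of change on treatment and ranks of baseline) as both fallback and robustness test.
2. State that Shapiro-Wilk is applied to the ANCOVA residuals.
3. Keep the Hodges-Lehmann estimate and interval, labelled as not adjusted for baseline, and say that it is not the inversion of the rank-ANCOVA test and can disagree with its p-value. Substituting the ANCOVA interval as the fallback estimate is not advised: protocol 8.8 ties ANCOVA or a mixed model to normality being met.
4. For Part 2, do not replace one analysis with the other. Report baseline-adjusted and unadjusted results side by side, labelled as such and as non-randomised evidence.

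The cost is SAP wording, one different procedure call and a revised non-parametric table shell. The statistical downside is small: the Part 1 fallback loses a matched test and interval.
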